### **Activity 3 population will be operationalized as follows:**

- To determine if a patient has a diagnosis of one of the above cancer types, use ICD-10 diagnosis codes: 15.0-16.99 (esophago-gastric) C17.0-C21.9 (small int. colorectal) C22.0-24.9 (hepatobiliary) C23-C25.9 (pancreas), C34-34.9: lung, C53.0-53.9 (cervix) C54-54.9 (uterine) and/or C56-57.9 (ovarian). When it comes time to execute, this list may be modified. CPT and procedure codes and EPIC's OPTIME operating room scheduling module will be used to determine if a patient is scheduled for a priority surgery.

**Mode of Participation:** Patients will have a *choice* of their preferred mode of eSyM participation and switching can be accommodated. Patients with a smart phone will be offered that approach first. Alternatives include participation in eSyM via any web-enabled device (laptop/tablet/desktop). Patients may designate a caregiver willing to elicit their symptoms and

report responses on their behalf (proxy reporting). This flexibility facilitates the intervention's reach to frail patients who may be those most likely to benefit. As needed, patients will also be offered eSyM training through in-person, phone, and/or virtual visits.

**Number of subjects (per site and overall):** For Activity 3, user acceptability testing (UAT) will be done with up to 390 patients from up to 6 participating sites. At the lead site (Dana-Farber), we anticipate conducting UAT with 90 participants distributed as follows: 15 patients from each cancer/type modality combination (15 thoracic surgical, 15 gynecologic surgical, 15 GI surgical, 15 thoracic medical oncology, 15 gynecologic medical oncology, and 15 GI medical oncology). We anticipate that at each of the 5 remaining participating sites, each site will conduct UAT with up to 60 participants distributed as follows: 10 patients from each cancer/type modality combination (10 thoracic surgical, 10 gynecologic surgical, 10 GI surgical, 10 thoracic medical oncology, 10 gynecologic medical oncology, and 10 GI medical oncology). Protocol does not mandate equal distribution of participants among participating sites. If a site is running behind or facing lower than anticipated accrual to the activity, then the other sites may enroll additional participants to make up the difference until the study wide UAT goal has been reached. The numbers referenced above are meant to serve as an estimate and sites may suspend or continue UAT as needed.

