**Materials that will be used to recruit subjects:** None.

**Duration anticipated to enroll all study subjects:** We anticipate that it will take three months prior to eSyM launch at each site to enroll all UAT/pilot participants, but the actual duration may vary.

**Monitor subjects for safety or minimize risks:** The risk to participants is minimal with the primary risk being loss of confidentiality/privacy. To monitor the risk of loss of confidentiality/privacy, the informatics/IT team will routinely monitor eSyM and investigate inquiries from study teams. Furthermore, patients who report severe symptoms will be prompted to call their clinic immediately, and clinicians will receive in-basket notifications in the Epic EHR of the severe symptom report.

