### **Activity 3a: eSyM Usage**

#### **Human Subjects Research Category (NHSR, exempt, expedited, full review): NHSR/QI**

Because eSyM will be implemented at each site *for use in routine clinical care and because this is a quality improvement (QI) activity, this is not human subjects research.*

**Informed Consent: Waiver of consent.** When a patient becomes eligible for eSyM, he/she/they will receive an automated welcome message, which includes an electronic disclaimer that contains important information about the purpose of eSyM, how/when it should be used, and what it does and does not communicate to their care team (see Appendices N & Q).

**Methods that will be used to identify potential subjects:** Access to eSyM will be automated. EPIC will automatically deliver the invitation to use eSyM to all patients defined above (See Section: “Activity 3 population will be operationalized as follows”).

**Duration of subject’s participation in the study:** Per protocol, eSyM usage continues for up to 60-180 days from their trigger event (i.e., new chemotherapy treatment plan and/or surgery), but extended use of eSyM is at the discretion of the site and each patient participant.

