### **Activity 3b: User Acceptability Testing (UAT)**

**Informed Consent: Waiver of documentation of consent.** Before observing the patient using eSyM, the patient will be provided with a letter (see appendix O) with the elements of informed consent, as well as the option not to be observed. They will be notified that participation is completely voluntary and can be stopped at any time for any reason. This activity is minimal risk.

**Methods that will be used to identify potential subjects:** Under a HIPAA waiver, study staff will look in the scheduling views of the electronic medical record and scheduling systems to identify potential participants. Study staff may also query Epic, administrative/operations/billing databases, order entry databases, and/or cancer registry databases to identify potential participants. Study staff may also accept potential patient referrals from site clinicians. Purposive sampling based on data from the electronic medical record (e.g., demographics, cancer stage, number of recent hospitalizations, number of prescription drugs) will be used to ensure that perspectives of diverse patients are included. Ideally, sites will use the developed eSyM reporting workbench reports in Epic to automatically pull a patient list for UAT.

**When, where, and how potential subjects will be recruited:** The clinical/study staff will approach the patient to see if they would be interested in participating in UAT. If a patient is interested in participating, the site will present the participant with a study letter and then begin observations. Patients may be approached in-person, via phone, via email or through a virtual visit.

**Description of procedures being performed for UAT:** Surgical patients will be set up to use eSyM at the time of surgical discharge (or at the site's discretion). Medical oncology patients will be set up to use eSyM at the time of their first chemotherapy dose visit (or at the site's discretion). The study staff will observe the patient accessing eSyM, the patient being trained on how to use eSyM, the patient using eSyM to do their first symptom reporting session.

**Duration of subject's participation in the study:** Per protocol, UAT observation will last approximately 30 minutes or less.

**What data will be collected and how:** The study staff will write down their observations as well as staff/patient feedback (see appendix P).

**Study design:** User acceptability testing.

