**Defining and operationalizing the denominator:**

- To determine if a patient has a diagnosis of one of the priority cancer types, use ICD-10 diagnosis codes: 15.0-16.99 (esophago-gastric) C17.0-C21.9 (small int. colorectal) C22.0-24.9 (hepatobiliary) C23-C25.9 (pancreas), C34-34.9: lung, C53.0-53.9 (cervix) C54-54.9 (uterine) and/or C56-57.9 (ovarian). When it comes time to execute, this list may be modified. CPT and procedure codes as well as EPIC operating room scheduling lists will be used to determine if a patient is scheduled for a priority surgery.
- Participants assigned to eSyM+ may be trained to use eSyM by their local clinic/study staff. Surgical patients may be trained to use eSyM at the time of surgical discharge (or at the site's discretion patients may receive training in how to use eSyM at a preoperative visit). Med Onc patients may be trained to use eSyM at the time of their first chemotherapy dose visit or at the time of a pre-treatment visit for chemotherapy teaching (at the site's discretion). Epic reports may also be used to identify eligible patients who are assigned or will be assigned to eSyM so that training of the eligible patients can be done by study research staff via telephone or email before or after beginning treatment or having surgery.
- Participants in the eSyM- cohort will meet priority population criteria and be seen at a participating site between 1/1/2018 and the site's eSyM go-live date. Participants in the eSyM+ cohort will meet priority population criteria and be seen at a participating site after their eSyM go-live date through March 31, 2024.

**Mode of Participation:** Patients will have a *choice* of their preferred mode of eSyM participation and switching can be accommodated. Patients with a smart phone will be offered that approach first, however all patients will be notified that access to eSyM is available as long as they can access the secure patient portal (MyChart). eSyM can be accessed securely through the MyChart portal on any web-enabled device. Alternatives to smart phone reporting include

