## 10.0 Study Endpoints and Statistical Analyses

**The detailed protocol statistical analysis plan (SAP) can be found in Appendix TT.**

### Analysis of activity 1 (stakeholder engagement):

Quantitative interviews will be scored using their established scoring metrics:

- The NOMAD instrument is a 23-item survey that measures implementation processes from the perspective of professionals directly involved in the work of implementing complex interventions in healthcare. [Appendix J]
- The AIM (Acceptability of Intervention Measure), IAM (Intervention Appropriateness Measure), and FIM (Feasibility of Intervention Measure) instruments are four-item measures of implementation outcomes that are often considered “leading indicators” of implementation success. [Appendix G]
- The CSAT (Clinical Sustainability Assessment Tool) instrument is a 49-item survey with 7 domains used by evaluators and researchers to determine the extent to which a practice is being implemented effectively. (Appendix Y)
- The ORCA (Organizational Readiness to Change Assessment) instrument is a 74-item survey with three domains, each item has been mapped to a CFIR construct, and will be scored according to Helfrich et al.'s (2009). [Appendix B]
- The OCM (Organizational Change Manager) instrument is a 60-item survey with 15 domains, each item has been mapped to a CFIR construct, and will be scored according to Gustafson et al.'s (2003). [Appendix B2]

Qualitative interviews (audio recordings and notes) will be evaluated for common themes. Results from the qualitative and quantitative interviews and surveys will be used to inform eSyM, its content, its rollout, and the training materials.

Analysis of Activity 3 (UAT/Pilot study):

Study staff will observe patient/proxy, clinician and clinical support staff action steps and interactions with the system. Observations will be recorded and used to refine eSyM, its rollout, and the training materials.

Any patient data collected will be analyzed as per the analysis plan for the stepped-wedge cluster randomized trial described below.

Analysis of Activity 4 (stepped-wedge trial):

*Additional details can be found in Appendix TT. Please reference Appendix TT for the most updated SAP.*

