4.2. General Analytic Approach

[figure not shown]
Medical Oncology and Surgery:

- The primary analysis will include data from both medical oncology (MO) and surgery (Surg) and estimate a common effect of the intervention in MO and SO. An indicator variable (MO vs. Surg), interaction between MO/Surg and Site, and interaction between MO/Surg and background time trend will be included as covariates for adjustment in multilevel generalized linear regression models.
- As a secondary analysis, for each outcome, the heterogeneity of the intervention effect by MO/Surg will also be assessed by the test for interaction between the intervention (eSym yes/no) and MO/surg using multilevel generalized linear regression models. In this analysis, the interaction between the intervention and MO/Surg will be added to the model for the primary analysis.
- As another secondary analysis, we will analyze the data from MO and Surg separately and estimate the intervention effect for each outcome. Note that this analysis is similar to the aforementioned secondary analysis including the interaction between the intervention and MO/Surg. While the aforementioned secondary analysis assumes common effects of patients' characteristics (such as age, race, gender and so on) across MO and Surg, this analysis consider these are possibly different between MO and Surg.

Determination of the intervention and length of follow-up for each episode:

- The presence /absence of the intervention (eSym+ vs. eSym-) is determined in a cross-sectional way at the time of the occurrence of the trigger event
- The follow-up period for each episode is one year from the chemotherapy start date (**MO**) and the date of discharge (**Surg**)

- The intervention determined at the trigger event will never change during the one-year of follow-up period unless another trigger event occurs (see Figure below)

- Some subjects may experience more than one trigger event (i.e., a new chemotherapy treatment plan for **MO** and a qualifying procedure for **Surg**) during the study. Thus, potentially, multiple data points/episodes will be collected from one patient.
- The primary analysis will include all these episodes other than the following episodes:
 - MO episode where its trigger event occurred after the patient was exposed to eSyM Surg, but before eSyM MO was rolled out in the patient's site.

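### No rule keeps Activity 3 pilot users of eSyM out of the eSyM- control group; if eSyM works, the primary EDTR Day 30 effect is biased toward no effect, by an amount the documents leave uncertain

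*Protocol*

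**What the plan says.** **Who is a control.** Protocol 5.0, Activity 4 (denominator): "Participants in the eSyM- cohort will meet priority population criteria and be seen at a participating site between 1/1/2018" and the site's go-live date. No never-exposed condition is attached. SAP 4.2 assigns eSyM+ or eSyM- cross-sectionally, at the trigger event. The June 2024 addendum makes the primary control set all first eligible episodes under the control condition.

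**Who is in the pilot.** Protocol 5.0, Activity 3: "user acceptability testing (UAT) will be done with up to 390 patients from up to 6 participating sites". That is 90 at the lead site and up to 60 at each of five others, split equally between surgery and medical oncology (MO) and across the three tumour groups. On timing: "We anticipate that it will take three months prior to eSyM launch at each site to enroll all UAT/pilot participants", with a caveat that the duration may vary. Activity 3b has staff observe "the patient using eSyM to do their first symptom reporting session". Activity 3a adds that "eSyM usage continues for up to 60-180 days from their trigger event".

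**What is excluded.** SAP 4.2 removes an "MO episode where its trigger event occurred after the patient was exposed to eSyM Surg" if eSyM MO was not yet live at the site, and the mirror case of a surgical episode after eSyM MO. The addendum restates the contamination exclusion only for the all-episode sensitivity analysis.

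**How pilot data are handled.** Protocol 10.0, Analysis of Activity 3: "Any patient data collected will be analyzed as per the analysis plan for the stepped-wedge cluster randomized trial described below".

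**What control is meant to be.** The acronym list calls eSyM- patients those assigned not to use eSyM. Activity 4 item 3 describes controls as not assigned to it. The PICOTS table gives the control condition as no eSyM symptom reporting.

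**The concern.** A pilot patient belongs to the priority population, has a trigger before go-live, and files at least one report. Under SAP 4.2, one report makes an episode engaged with eSyM. Use can run well past Day 30, so it covers the primary outcome window. The date-based rule nevertheless labels this patient unexposed.

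The SAP already accepts that eSyM exposure through the other cohort disqualifies a control episode. Direct exposure in the same cohort is at least as contaminating, yet no rule covers it.

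If eSyM reduces EDTR, exposed controls lower the control rate and shrink the contrast. The planned effect is only 3 to 4 percentage points (SAP 4.7), and no planned sensitivity analysis isolates pilot exposure.

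**Working it through.** **Step 1: trace a pilot patient through the rules.** Take an MO patient at a site where neither cohort is live, enrolled in the pilot at the first chemotherapy visit.
- Meets the priority criteria (Activity 3 and Activity 4 populations; SAP 3.2): yes.
- Trigger before go-live, so eSyM- (SAP 4.2): yes.
- Excluded as MO after eSyM Surg exposure: no. Excluded as Surg after eSyM MO: no.
- First episode, so in the addendum's primary set: yes, unless an earlier episode exists.

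The patient is analysed as a control. The existing rules could catch only a later episode in the other cohort, which the first-episode primary does not use.

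**Step 2: reproduce the planned totals.** 12 per month × 6 months × 7 periods × 6 sites × 2 cohorts = 6,048, as in SAP 3.3. With one MO and one surgical go-live at each of the six steps, mirrored within site, control cells number 2 × (1+2+3+4+5+6) = 42, and 42 × 72 = 3,024. This agrees with the SAP's aim of equal control and intervention numbers. Pilot total: 90 + 5 × 60 = 390.

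**Step 3: pilot share of controls.**
- SAP period table (from March 2019): 390/3,024 = 12.9%.
- Protocol window (from 1/1/2018): 14 more months × 12 × 12 site-cohorts = 2,016, so 390/5,040 = 7.7%.

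A crude arm comparison would shrink by the first share: 3.0 × (1 − 0.129) = 2.61 points, and 4.0 × (1 − 0.129) = 3.48 points.

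**Step 4: the stepped-wedge contrast.** After adjustment for site and calendar time, the bias depends on where the pilot patients fall relative to crossover. I used a noise-free weighted regression on monthly cells with live status, site × cohort and time × cohort terms. Time was either period or a natural cubic spline; the length was 42 or 48 months. The true effect was set to 1 in live cells. In pilot months it was set to the exposed fraction: 30 pilot patients of 36 accrued over three months (83%) in a non-lead site-cohort, and 45 of 36, capped at 1, at the lead site. With the cap, 372 pilot patients are counted. Pilot use is assumed to give the full benefit.

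| Placement and size of pilot | Fraction of true effect recovered |
|---|---|
| Three months before each cohort's own go-live, all pilot patients, minimum accrual | 0.65-0.71 |
| Same placement, half the pilot or twice the accrual | 0.82-0.85 |
| Three months before each site's first launch, all pilot patients, minimum accrual | 0.84-0.88 |
| Three months before the first launch anywhere, all pilot patients, minimum accrual | 0.96-1.00 |

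For a true effect of 3 to 4 points:
- first row: about 2.0 (0.65 × 3) to 2.8 (0.71 × 4);
- third row: about 2.5 (0.84 × 3) to 3.5 (0.88 × 4);
- last row: about 2.9 (0.96 × 3) to 4.0 (1.00 × 4).

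**The case against.** **Intent.** The acronym list, Activity 4 item 3 and the PICOTS table all describe controls whom a pilot user would not resemble. SAP 4.6 also speaks generally of contaminated eSyM- episodes. A reader might therefore infer that the team has decided to count pilot users as controls, and the documents do not support that: the text is inconsistent. But none of these descriptions is a step that removes anyone. The contamination wording points back to the two cross-cohort rules. The never-exposed safeguard in Activity 4 covers survey controls only. Counting Activity 3 accrual separately in Protocol 6.0 does not remove patients from a control group built by Epic query.

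**Size.** A reader might infer that about a third of the effect is lost. That needs four things together: all 390 pilot patients, full benefit, minimum accrual, and each cohort piloted just before its own go-live.
- The protocol ties pilot timing to launch at each site, not to each cohort, and planned go-lives within a site differ by up to 30 months.
- Activity 3 and the study design text in Protocol 10.0 put piloting before the trial itself.
- The 390 is a ceiling, sites may suspend UAT, and the pilot's purpose was to refine the system, so full benefit is doubtful.
- SAP 3.3 calls the accrual rate highly conservative, and Activity 5 already reports more than 13,000 patients.

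This objection stands, and the size must be given as a range.

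**Pilot data sentence.** The sentence in Protocol 10.0 can mean only that the same methods apply. It does not show that pilot patients are pooled as controls. This also stands.

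**Conclusion.** The definitional gap holds: as written, a pilot patient's same-cohort first episode with a pre-go-live trigger enters the primary analysis as eSyM-. If eSyM works, the bias is toward no effect.

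The size is uncertain. The recovered fraction runs from about 0.65 in the worst case to 1.00 if all piloting came before the first launch anywhere. The intermediate readings fall at about 0.82-0.88. These figures rest on the planned schedule, even accrual, and pilot use as effective as routine use. Fewer pilot patients, weaker benefit or higher accrual would reduce the loss. Exposure could instead exceed 390 if the automated invitation described in Activity 3a ran before go-live. The documents do not settle how many patients were piloted or when, so no single value should be quoted as the expected loss.

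**What to change.** In Protocol 5.0 (denominator), SAP 4.2 and the addendum, add a third exclusion: any pre-go-live episode of a patient who was given eSyM access or submitted an eSyM report in Activity 3. Apply it to the eSyM- primary population and to Group C, so that the matched comparison with engaged patients is covered too. Report the number excluded by site and cohort. In Protocol 10.0, Analysis of Activity 3, state that pilot data are not pooled as controls.

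The data exist. No PHI is collected during UAT observation itself, but Activities 3a and 3c collect eSyM usage from Epic and abstract the records of all UAT/pilot patients. If sites already left these patients out, the sentence documents that.

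The cost is lost control episodes: up to 390 if exposure was confined to UAT patients (3,024 − 390 = 2,634 left at minimum accrual), possibly more if the automated invitation ran early. A sensitivity analysis dropping all episodes triggered in the three months before each site-cohort's go-live is optional. It would avoid relying on individual pilot records, and Activity 3b sampled UAT patients purposively.

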**Duration of subject's participation in the study:**

- 1) Per protocol, eSyM usage continues for up to 60-180 days but can continue indefinitely at the site's discretion.
- 2) The SASS Questionnaire is a one-time, 20-minute survey administered 30-180 days after surgery or first dose of chemotherapy.
- 3) The patient qualitative interview(s) will last approximately 30 (but no more than 120) minutes; they will be administered any time after eSyM assignment at a time that is convenient for the subject.
- 4) All eSyM- control and eSyM+ intervention patients will be followed for outcomes for up to 1-year after the trigger event (i.e., new chemotherapy treatment plan and/or surgery).

**Duration anticipated to enroll all study subjects:** We anticipate that it will take five years to complete this activity.

**Study design:** Hybrid effectiveness-implementation stepped-wedge cluster randomized trial.

**Description of all research procedures being performed:**

- a) Epic, administrative/operations/billing databases, order entry databases, and/or cancer registry databases may be queried to identify denominator patients under a HIPPA waiver.
- b) Patients assigned to eSyM+ will be set up to use eSyM by their local clinic/study staff. Surgical patients will be set up to use eSyM at the time of surgical discharge (or at the site's discretion). Medical oncology patients will be set up to use eSyM at the time of their first chemotherapy dose visit (or at the site's discretion).
- c) Select eligible participants will receive a message inviting them to participate in the SASS questionnaire 30-days after surgery or first chemo dose (Appendix Z).
- d) Participants who participate in the SASS questionnaire and indicate that they wish to receive a gift card will receive \$15 gift card. Gift cards will be mailed or emailed according to patient preference. Please note, emailed gift cards will come directly from Amazon.com or sent by a study research staff member.

- e) Participants who participate in the qualitative interviews and indicate that they wish to receive a gift card will receive a \$15 gift card. Gift cards will be mailed or emailed according to patient preference. Please note, emailed gift cards will come directly from Amazon.com or sent by a study research staff member.
- f) All denominator patients (eSyM- control and eSyM+ intervention) will undergo medical record (and/or local cancer registry) reviews. The medical record (and/or local cancer registry) reviews will be accomplished using both automated data extraction and manual data abstraction under a HIPAA waiver.

**Monitor subjects for safety or minimize risks:** The risk to participants is minimal with the primary risk being loss of confidentiality/privacy. To monitor the risk of loss of confidentiality/privacy, the informatics team will routinely monitor eSyM reports and data extracts and investigate inquiries from study teams. Furthermore, patients who report severe symptoms will be prompted to call their care team immediately, and clinicians will receive in-basket notifications in the Epic EHR of the severe symptom report. All interview participants from outside of Dana-Farber Cancer Institute will provide written consent to have their information shared with the Dana-Farber research staff members who will contact them to conduct the interviews.

